#### 5.2.1 Dose Selection/Modification

#### 5.2.1.1 Dose Selection

The rationale for selection of doses to be used in this trial is provided in Section 4.0 - Background and Rationale.

Details on preparation and administration of pembrolizumab (MK-3475) are provided in the Pharmacy Manual.

#### 5.2.1.2 Dose Modification

Adverse events (both non-serious and serious) associated with pembrolizumab exposure may represent an immunologic etiology. These adverse events may occur shortly after the first dose or several months after the last dose of treatment. Pembrolizumab must be withheld for drug-related toxicities and severe or life-threatening AEs as per **Table 7** below. See Section 5.6.1 and Events of Clinical Interest Guidance Document for supportive care guidelines, including use of corticosteroids.

Table 7. Dose Modification Guidelines for Drug-Related Adverse Events

Toxicity	Hold Treatment For Grade	Timing for Restarting Treatment	Discontinue Subject
Diarrhea/Colitis	2-3	Toxicity resolves to Grade 0-1.	Toxicity does not resolve within 12 weeks of last dose or inability to reduce corticosteroid to 10 mg or less of prednisone or equivalent per day within 12 weeks.
	4	Permanently discontinue	Permanently discontinue
AST, ALT, or Increased Bilirubin	2	Toxicity resolves to Grade 0-1	Toxicity does not resolve within 12 weeks of last dose.
	3-4	Permanently discontinue (see exception below) 	Permanently discontinue
Type 1 diabetes mellitus (if new onset) or Hyperglycemia	T1DM or 3-4	Hold pembrolizumab for new onset Type 1 diabetes mellitus or Grade 3- 4 hyperglycemia associated with evidence of beta cell failure.	Resume pembrolizumab when patients are clinically and metabolically stable.
Hypophysitis	2-3	Toxicity resolves to Grade 0-1	Toxicity does not resolve within 12 weeks of last dose or inability to reduce corticosteroid to 10 mg or less of prednisone or equivalent per day within 12 weeks.
	4	Permanently discontinue	Permanently discontinue
Hyperthyroidis m	3	Toxicity resolves to Grade 0-1	Toxicity does not resolve within 12 weeks of last dose or inability to reduce corticosteroid to 10 mg or less of prednisone or equivalent per day within 12 weeks.
	4	Permanently discontinue	Permanently discontinue
Hypothyroidism	2-4	Therapy with pembrolizumab can be continued while treatment for the thyroid disorder is instituted	Therapy with pembrolizumab can be continued while treatment for the thyroid disorder is instituted.
Infusion Reaction	3-4	Permanently discontinue	Permanently discontinue
Pneumonitis	2	Toxicity resolves to Grade 0-1	Toxicity does not resolve within 12 weeks of last dose or inability to reduce corticosteroid to 10 mg or less of prednisone or equivalent per day within 12 weeks.
	3-4	Permanently discontinue	Permanently discontinue
Renal Failure or Nephritis	2	Toxicity resolves to Grade 0-1	Toxicity does not resolve within 12 weeks of last dose or inability to reduce corticosteroid to 10 mg or less of prednisone or equivalent per day within 12 weeks.
	3-4	Permanently discontinue	Permanently discontinue
All Other Drug- Related Toxicity 	3 or Severe 	Toxicity resolves to Grade 0-1	Toxicity does not resolve within 12 weeks of last dose or inability to reduce corticosteroid to 10 mg or less of prednisone or equivalent per day within 12 weeks.
TOXICITY	4	Permanently discontinue	Permanently discontinue

Note: Permanently discontinue for any severe or Grade 3 drug-related AE that recurs or any life-threatening event.

<sup>1 For patients with liver metastasis who begin treatment with Grade 2 AST or ALT, if AST or ALT increases by greater than or equal to 50% relative to baseline and lasts for at least 1 week then patients should be discontinued.

to 50% relative to baseline and lasts for at least 1 week then patients should be discontinued.

Patients with intolerable or persistent Grade 2 drug-related AE may hold study medication at physician discretion. Permanently discontinue study drug for persistent Grade 2 adverse reactions for which treatment with study drug has been held, that do not recover to Grade 0-1 within 12 weeks of the last dose.

Grade 3 drug-related amylase or lipase abnormality that is not associated with symptoms or clinical manifestations of pancreatitis

Toxicity	Hold Treatment For Grade	Timing for Restarting Treatment	Discontinue Subject
does not require	e dose delay.		

Dosing interruptions are permitted in the case of medical / surgical events or logistical reasons not related to study therapy (e.g., elective surgery, unrelated medical events, patient vacation, and/or holidays). Subjects should be placed back on study therapy within 3 weeks of the scheduled interruption, unless otherwise discussed with the Sponsor. The reason for interruption should be documented in the patient's study record.

## 5.2.2 Timing of Dose Administration

Trial treatment should be administered on Day 1 of each cycle after all procedures/assessments have been completed as detailed on the Trial Flow Chart (Section 6.0). There is a ±7 day treatment window for Day 1 of each cycle.

All trial treatments will be administered on an outpatient basis.

Pembrolizumab 200 mg will be administered as a 30 minute IV infusion every 3 weeks. Sites should make every effort to target infusion timing to be as close to 30 minutes as possible. However, given the variability of infusion pumps from site to site, a window of -5 minutes and +10 minutes is permitted (i.e., infusion time is 30 minutes: -5 min/+10 min).

The Pharmacy Manual contains specific instructions for the preparation of the pembrolizumab infusion fluid and administration of infusion solution.

Vorinostat should be taken with food, at regular intervals regardless of pembrolizumab infusion time. On days the pt receives pembrolizumab, the vorinostat should be taken prior to pembrolizumab infusion.

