## **6.0 TRIAL FLOW CHART**

## 6.1 Study Flow Chart\*

Trial Period:		Treatment Cycles								End of Treatment	Post-Treatment		
	Study					To be		ated be	eyond		Safety		Survival
Treatment Cycle/Title:	Screening (Visit 1)	1	2	3	4	5	6	7	8	Discon	Follow- up	Follow Up Visits	Follow- Up
Scheduling Window (Days):	-27 to c1d1 e		± 7	± 7	± 7	± 7	± 7	± 7	± 7	At time of Discon	30 days post last dose of study drug	Every 8 weeks post discon	Every 12 weeks
Screening Consent	Χ												
Informed Consent	Х												
Inclusion/Exclusion Criteria	Х												
Demographics and Medical History	Х												
Prior and Concomitant Medication Review	Х	Х	Х	х	Х	Х	х	Х	Х				
Vorinostat compliance review/Pill Diary		Х	Х	х	Х	Х	Х	Х	Х	Х			
Trial Treatment Administration		Х	Х	Х	Х	Х	Х	Х	Х				
Post-study anticancer therapy status										×	Х		Х
Survival Status		Х	Х	Х	Х	Х	Х	Х	Х	Х			Х
Review Adverse Events	Χ †	Х	Х	Х	Х	Х	Х	Х	Х	Х	Х		
Full Physical Examination	Х												
Directed Physical Examination		Х	Х	Х	Х	Х	Х	Х	Х	Х	Х		
Vital Signs and Weight	Х	Х	Х	Х	Х	Х	Х	Х	Х	Х	Х		
ECOG Performance Status	Х	Х	Х	Х	Х	Х	Х	Х	Х		Х		
Pregnancy Test – Urine or Serum b-HCG	Х	Х	Х	Х	Х	Х	Х	Х	Х		Х		

Trial Period:					Cycle	es				End of Treatment	Post-Treatment		
	Study					To be		ated be	eyond		Safety		Survival
Treatment Cycle/Title:	Screening (Visit 1)	1	2	3	4	5	6	7	8	Discon	Follow- up	Follow Up Visits	Follow- Up
Scheduling Window (Days):	-27 to c1d1 e		± 7	±7	± 7	±7	± 7	± 7	± 7	At time of Discon	30 days post last dose of study drug	Every 8 weeks post discon	Every 12 weeks
PT/INR and aPTT	Х	X (C1D15 -C1D21											
CBC with Differential	Х	Х	Х	Х	Х	Х	Х	Х	Х		Х		
Comprehensive Serum Chemistry Panel	Х	Х	Х	х	Х	Х	Х	Х	Х	Х	Х		
Magnesium	Х	Х	Х	Х	Х	Х	Х	Х	Х	Х	Х		
Urinalysis	Х												
T3, FT4 and TSH	Х	Х	Х	Х	Х	Х	Х	Х	Х	Х	Х		
Echocardiogram g	Х												
EKG	Х												
Tumor Imaging (CT Thorax/Abdomen)	Х			Х		Х		Х		Х		X d	
Brain MRI or Brain CT	Х												
Archival or Newly Obtained Tissue Collection a,b	Х	X (C1D15 -C1D21											
Correlative Studies Blood Collection c	X c	X c		Х		Х		Х		Х		Х	

Trial Period:		Treatment Cycles						End of Treatment	Po	st-Treatme	nt		
	Study					To be		ated be	yond		Safety		Survival
Treatment Cycle/Title:	Screening (Visit 1)		2	3	4	5	6	7	8	Discon		Follow Up Visits	Follow- Up

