Scheduling Window (Days):	-27 to c1d1 e		± 7	± 7	± 7	± 7	± 7	± 7	± 7	At time of Discon	30 days post last dose of study drug	Every 8 weeks post discon	Every 12 weeks

\*All clinic visits and tests (including labs, imaging studies and biopsies) will have a plus or minus 7 day window for completion.

<sup>a All patients in the study are required to have a pre-treatment biopsy, where feasible, or archival tissue from after the most recent line of therapy, which will be tested for PD-L1 and nanostring analyses.

<sup>b C1D15-21 biopsies will be done on patients in the phase I dose escalation, phase Ib and phase II parts of the study, where feasible. PD-L1 and Nanostring studies will be completed on all of these biopsy specimens.

<sup>c Timepoints for the first two correlative study blood collection include first during Screening or on C1D1, and second on C1D15. The remainder of the blood collections will occur with the reimaging scans. Histone acetylation studies will be run on serial PBMC draws in all patients (includes phase I dose escalation, phase Ib expansion and phase II). The blood will be collected in five 10 mL green top (sodium heparin) tubes for a total of about 50mL of whole blood.

<sup>d Subjects who discontinue trial treatment for a reason other than disease progression will move into the Follow-Up Phase and should be assessed every 8 weeks (56 ± 7 days) by radiologic imaging to monitor disease status. After 1 year, the imaging time point will occur every 12 weeks (± 7 days).

<sup>e The main study screening window will occur within 28 days prior to the first study treatment. Note additionally that screening laboratory blood and urine studies must be obtained within 10 days of C1D1, with the exception of pregnancy testing in applicable patients, which must be obtained within 72 hours of first treatment.

f Only serious adverse events will be collected during the screening window.

<sup>9 Echocardiogram will be performed at screening for baseline, and may be repeated if clinically indicated per the treating investigator. Echocardiogram should be performed within 30 days of treatment initiation.

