**Table 9. Laboratory Tests** 

Hematology	Chemistry	Urinalysis	Other
Hematocrit	Albumin	Blood	Serum β-human chorionic gonadotropin†
Hemoglobin	Alkaline phosphatase	Glucose	(β-hCG)†
7.1.5.1.1 Pplatelet count	Alanine aminotransferase (ALT)	Protein	PT (INR)
WBC (total and differential)	Aspartate aminotransferase (AST)	Specific gravity	aPTT
Red Blood Cell Count		Microscopic exam (If abnormal)	Total thriiodothyronine (T3)
Absolute Neutrophil Count	Carbon Dioxide ‡	results are noted	Free tyroxine (T4)
Absolute Lymphocyte Count	(CO 2 or biocarbonate)	Urine pregnancy test †	Thyroid stimulating hormone (TSH)
	Calcium		
	Chloride		Blood for correlative studies
	Glucose		
	Potassium		
	Sodium		
	Magnesium		
	Total Bilirubin		
	Direct Bilirubin (If total bilirubin is elevated above the upper limit of normal)		
	Total protein		
	Blood Urea Nitrogen		

† Perform on women of childbearing potential only. If urine pregnancy results cannot be confirmed as negative, a serum pregnancy test will be required. ‡ If considered standard of care in your region.

Laboratory tests for screening or entry into the Second Course Phase should be performed within 10 days prior to the first dose of treatment. Any screening labs done within 7 days of C1D1 do not need to be repeated prior to first treatment. After Cycle 1, pre-dose laboratory procedures can be conducted up to 72 hours prior to dosing. Results must be reviewed by the investigator or qualified designee and found to be acceptable prior to each dose of trial treatment.

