## 8.2.2 Definitions for Dose Limiting Toxicities.

The period for evaluating DLTs is defined as the time period starting with the first dose of investigational products until the planned administration of the second dose of pembrolizumab. Subjects are considered evaluable for assessment of DLTs if they receive at least 75% of the protocol assigned doses of both pembrolizumab and vorinostat and complete the safety follow-up through the end of the DLT evaluation period, or experience a DLT during the DLT evaluation period.

Subjects who do not remain on the study up to this time for reasons other than DLT will be replaced with another subject at the same dose level. DLTs will be graded according to the National Cancer Institute Common Terminology Criteria for Adverse Events (NCI CTCAE v4.03). A DLT will be defined as any Grade 3 or higher toxicity that occurs during the DLT evaluation period. Toxicity that is clearly and directly related to the primary disease or to another etiology is excluded from this definition.

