#### 8.2.3 Dose escalation.

The maximum tolerated dose (MTD) is defined as the dose with the DLT rate of 30%. Starting at the first dose level of 200mg PO daily, if there are < 1 DLT then it is acceptable to escalate to the next dose level. If no DLT is observed at the first dose level (200mg PO daily) with 3 subjects, then dose escalation will continue with dosing groups of 3 subjects at a time. This will continue up to dose level 2 (400mg of vorinostat). The DLT assessment period is the first 21 days of treatment.

If a DLT is observed at 200 mg PO daily, then the vorinostat dose will be de-escalated to 100 mg PO daily with the intent of increasing the dose back to 200 mg PO daily if 100 mg PO daily is shown to be safe and well-tolerated. After the first DLT is observed or any proposed dose level is achieved without any DLTs, subsequent dose assignments are guided by the modified continuous reassessment method (mCRM) as described below.

The mCRM works in the following way. If n subjects have been assigned and completed 21 days of follow-up, let Yi=1 if the ith subject experienced DLT and let Yi=0 otherwise, for i = 1,..., n. The mCRM model (O'Quigley et al. 1990) used here is

Prob(Yi=1|dose level k)= $\mathbf{F}(\theta, \text{dose level k}) = \exp(3 + \theta \times \text{dose}_{(k)}^*)/(1 + \exp(3 + \theta \times \text{dose}_{(k)}^*)$ 

where  $\theta$  is the parameter to be estimated for the model,  $\mathbf{F}$  is the probability of a subject i experiencing a DLT at dose level k, the dose(k)\* is the standardized dose. The prior distribution on parameter  $\theta$  is assumed to be a gamma distribution with shape=1 and scale=1. The Bayes' theorem is used to update the prior distribution of  $\theta$ . After each subject's response is observed, the mean posterior density of the parameter,  $\theta$ , is computed.

The dose to be administered to the next subject is the dose  $x_{n+1}$  such that  $|Prob(y=1| x_{n+1}, \theta^{(n)}) - 0.3|$  is minimized (i.e., the dose with the estimated DLT rate closest to the target rate of 0.3). When a dose is escalated, skipping dose levels is not allowed so that any escalation would only be to the next higher dose level in the predefined sequence. When a dose is deescalated, a dose level can be skipped.

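### In the dose escalation, the ±7 day window lets Cycle 2 Day 1 fall so late that no post-baseline CBC or chemistry is scheduled inside the 21-day DLT period

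*Combined protocol and SAP*

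**What the plan says.** **Timing of the second dose.** Section 5.2.2: "There is a ±7 day treatment window for Day 1 of each cycle". The footnote to the flow chart (Section 6.1) extends this to procedures: "All clinic visits and tests (including labs, imaging studies and biopsies) will have a plus or minus 7 day window for completion". Neither place makes an exception for the dose escalation.

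**Safety labs.** In the flow chart, the row "CBC with Differential" and the chemistry row have one entry per cycle, and the Cycle 1 entry carries no later-day tag. The items tagged for Cycle 1 Days 15-21 are PT/INR with aPTT and the tissue collection. Correlative research blood is due on Cycle 1 Day 15. The text under Table 9 (Section 7.1.5) adds: "After Cycle 1, pre-dose laboratory procedures can be conducted up to 72 hours prior to dosing". It also relaxes the baseline draw: "Any screening labs done within 7 days of C1D1 do not need to be repeated prior to first treatment".

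**DLT period and its use.** Section 8.2.3: "The DLT assessment period is the first 21 days of treatment". Section 8.2.2 ends the period at the planned second pembrolizumab dose. To be evaluable without a DLT, a patient must receive enough of both drugs and "complete the safety follow-up through the end of the DLT evaluation period". Section 8.2.3 then scores each patient who has completed 21 days as 1 for a DLT and 0 otherwise.

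**What hangs on one event.** Section 8.2.3: "If a DLT is observed at 200 mg PO daily, then the vorinostat dose will be de-escalated to 100 mg PO daily". With no DLT in three patients, the next cohort goes to 400 mg.

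**The concern.** Several DLT criteria in Section 8.2.2 can be met only if blood is drawn: transaminases above 8 × ULN, total bilirubin above 5 × ULN, and severe thrombocytopenia or neutropenia outside the listed exclusions. Section 4.2.1 itself links cytopenias to vorinostat, the drug being escalated.

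The DLT period is fixed, but the labs that reveal these events are tied to the second dose, which may move by a week either way. If C2D1 slips far enough, Day 21 passes with no scheduled post-baseline CBC or chemistry and the patient is still scored 0. An abnormality found at the late draw is then dated after the period. Since one DLT at the starting dose turns the next cohort down and none sends it up, patients in the same cohort should be judged on comparable labs.

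**Working it through.** **Inputs**
- C1D1 is Day 1. Pembrolizumab is given every 3 weeks, so nominal C2D1 is Day 22 (Section 5.2.2).
- Window on C2D1: ±7 days (Section 5.2.2).
- Pre-dose labs: 0 to 3 days before the dose (text under Table 9).
- DLT period: Days 1-21 (Section 8.2.3).
- Assumptions: the untagged Cycle 1 entry for CBC and chemistry means Day 1; days are whole calendar days; the flow chart's ±7 days for labs is not added on top of the 72-hour limit.

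**Step 1: permitted dates.** 22 − 7 = Day 15 to 22 + 7 = Day 29, which is 15 dates.

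**Step 2: is a scheduled post-baseline draw inside Days 1-21?** For C2D1 on Day d, the draw falls on Days d − 3 to d. It is always inside if d ≤ 21 and never inside if d − 3 > 21, that is d ≥ 25.

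| C2D1 on | Draw falls on | Draw by Day 21? | Dates |
|---|---|---|---|
| Days 15-21 | Days 12-21 | Always | 7 |
| Days 22-24 | Days 19-24 | Only if taken at least 1, at least 2, or exactly 3 days ahead, respectively | 3 |
| Days 25-29 | Days 22-29 | Never | 5 |

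7 + 3 + 5 = 15.

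**Step 3: sensitivity to Section 8.2.2.** If a draw on Day 22, the planned date of dose 2, is also accepted, the limits move by one day: always for Days 15-22 (8 dates), lead-dependent for Days 23-25 (3), never for Days 26-29 (4).

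**Step 4: the edges.**
- C2D1 on Day 15: last scheduled labs on Days 12-15, leaving 21 − 15 = 6 to 21 − 12 = 9 days of the period after them.
- C2D1 on Day 29: labs on Days 26-29, which is 26 − 1 = 25 to 29 − 1 = 28 days after a C1D1 draw. If screening labs taken 7 days before C1D1 replaced that draw, the gap reaches 28 + 7 = 35 days, and Days 1-21 contain no scheduled CBC or chemistry at all.

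**Step 5: the plan's own dose-selection figures.** The plan gives no figure for lab coverage. The nearest is Table 13, the probability of selecting the true MTD. I re-simulated the mCRM: logistic model with intercept 3, gamma(1,1) prior, posterior mean DLT probability, cohorts of 3, no upward skipping, 12 patients, 8,000 trials. The plan does not print the standardised doses. Setting dose* = (logit(initial guess) − 3)/ln 2, so that the initial guesses hold at the prior median, gives 10.7, 25.5, 28.7 and 30.1% at 400 mg through the Table 11 example, against 10.9, 25.5, 28.7 and 30.1% stated. Correct selection in Scenarios 1-4 is then 83.7, 54.9, 53.8 and 82.9%, against 83.3, 54.5, 53.2 and 83.5% stated. The plan's figures reproduce. My simulation counts every DLT that occurs; the documents give no share that would be missed, so no change in selection can be derived.

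**The case against.** The other side has real material.

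- Evaluability requires safety follow-up to the end of the period, and Section 7.1 allows unscheduled tests. But Section 8.2.2 names no lab, and unscheduled tests depend on the investigator seeing a clinical need.
- Sections 7.2 and 8.2.2 set aside lab abnormalities that are not clinically significant. This narrows the point to findings that cause symptoms, which should prompt a test, or that need treatment without symptoms. The second group remains: Table 7 and Section 5.6.1 call for permanent discontinuation and intravenous steroids for Grade 3-4 transaminase or bilirubin rises. I assume that transaminases above 8 × ULN fall in those grades, because the protocol does not print the CTCAE limits.
- Section 8.2.2 provides for repeat testing of significant lab findings and lets the sponsor and investigators declare unlisted events DLTs. Repeat testing needs a first result, and the second clause does not address timing.
- A delay caused by abnormal pre-dose labs already has labs behind it. That leaves mainly logistical delay, which Section 5.2.1.2 expressly permits, for example for vacation or holidays.
- Patients are seen late in Cycle 1 for coagulation tests, biopsy where feasible, and research blood. That is clinical contact, but not a CBC or chemistry.
- The single-agent vorinostat study in Section 4.2.1 saw no DLTs at 200 mg twice daily (14 days on, 7 off), the same daily total as the top dose here. This is reassuring but says nothing about the combination.

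Four stronger readings are tempting and are not supported.

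1. A reader might count early C2D1 dates as failures too, by asking for labs near the end of the period. The plan sets no such requirement; Days 15-21 always carry a draw inside the period, and nothing in the documents shows that Day 12-18 labs are worse at finding these toxicities.
2. A reader might infer that the DLT period itself moves with the window. Section 8.2.2 refers to the planned dose and Section 8.2.3 fixes 21 days.
3. A reader might infer that Table 13 is wrong or that the MTD will be biased. The table reproduces, and any shift would rest on an invented miss rate.
4. A reader might blame the window for all the sparse monitoring. Even on the nominal schedule there is no CBC or chemistry between C1D1 and Days 19-22.

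**Conclusion.** The point holds as a small operational gap in the dose escalation. Against the plan's own 21-day period, 5 of 15 permitted C2D1 dates leave no scheduled post-baseline CBC or chemistry inside it, 3 depend on the lead time, and 7 always have one. Accepting Day 22 makes this 4, 3 and 8. A patient with a logistically delayed second dose can be scored as no DLT without the labs on which hepatic and haematologic DLTs depend.

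The counts describe permitted dates, not how often they will occur, and concern at most 12 patients. They rest on reading the untagged Cycle 1 labs as Day 1 and on the 72-hour limit. No effect on mCRM selection is shown. The change is worth considering because it is cheap, not because the design fails without it.

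**What to change.** Make two changes, both limited to the phase I dose escalation.

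1. Flow chart: add CBC and chemistry to the PT/INR draw at Cycle 1 Days 15-21, to be done on Days 19-21 and before any second dose, required even if the second dose is delayed, and exempt from the ±7 day window.
2. Section 5.2.2: set the window for Cycle 2 Day 1 to 0/+7 days.

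With the second change the earliest dose 2 is Day 22, so the Day 19-21 draw always precedes it. It also keeps a second infusion out of the DLT period. That is a minor gain, since Section 4.2.2 reports pembrolizumab at up to 10 mg/kg every 2 weeks without DLTs.

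Cost: at most one extra routine blood draw per patient, and no early second dose in the escalation. If dose 2 is on time, the new draw can serve as the pre-dose draw, because Day 22 − Day 19 = 3 days is within the 72 hours. A separate draw is needed when dose 2 is on Day 25 or later, or when an early biopsy requires coagulation tests before Day 19.

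The change does not close the mid-cycle gap on the nominal schedule, and it does not schedule the repeat draws that the 3-day recovery rules in Section 8.2.2 need.
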